## 7.7 Safety Assessments

### 7.7.1 Adverse Events

Subjects will be monitored for AEs according to [Section 8](#).

If a subject experiences respiratory symptoms suggestive of SARS-CoV-2 infection, the subject should notify the clinical site for a visit to collect nasopharyngeal swabs for RT-PCR virus detection.

Subjects with positive ELISA anti-N IgG results without COVID-19 symptoms may indicate asymptomatic SARS-CoV-2 infection and will be followed with the appropriate standard of care. Subjects with a positive ELISA anti-N IgG result should have a PCR test and be followed until both are negative as in the protocol instructions ([Section 7.6](#)).

## **7.7.2                   Reactogenicity Assessments**

Subjects will keep a Diary Card to track reactogenicity assessments for 7 days after each vaccination. Reactogenicity assessments include generalized symptoms such as headache, fatigue, muscle pain, joint pain, nausea, chills, fever, and rash (not at injection site), and localized reactions including pain, erythema, induration, and swelling. If an AE continues after 7 days, the AE will be captured as ongoing/continuing (not noted as a new AE).

## **7.7.3                   Laboratory Tests**

A certified laboratory will be utilized to process and provide results for the clinical safety laboratory tests listed in [Table 7-1](#). The baseline laboratory test results for clinical assessment for a particular test will be defined as the last measurement prior to the first dose of study vaccine.

Subjects will fast a minimum of 8 hours prior to clinical laboratory sample collection at screening.

During the screening period, if a subject has an out-of-range value for a clinical safety laboratory parameter that the Investigator believes is not clinically significant or the Investigator does not believe is correct (eg, lab or specimen processing error), but the Investigator wants to confirm with a repeat laboratory test, a single repeat is allowed to confirm the initial result.

If Part C Expansion (optional) is performed, all Part C subjects will have safety laboratory tests performed at screening only in order to satisfy the inclusion/exclusion criteria. In addition, the first 200 subject in Part C will have safety laboratory tests performed at all time points. The remaining subjects in Part C will not have safety laboratory tests performed at any of the post-dose time points unless the Investigator deems it necessary.

Additional safety laboratory tests may be conducted as needed by the Investigator to evaluate subject safety.

**Table 7-1 Clinical Safety Laboratory and Screening Tests**

Hematology	Chemistry	Urinalysis	
Hematocrit Hemoglobin Red blood cell count White blood cell count Neutrophils (absolute) Lymphocytes (absolute) Monocytes (absolute) Basophils (absolute) Eosinophils (absolute) Platelet count (estimate not acceptable)	Albumin Alkaline phosphatase Alanine aminotransferase Aspartate aminotransferase Gamma glutamyl transferase Direct bilirubin Total bilirubin Lactate dehydrogenase Total protein	Blood urea nitrogen Creatinine Calcium Phosphate Sodium Potassium Carbon dioxide Chloride Glucose a Total cholesterol Triglycerides a	Specific gravity Ketones pH Protein Blood Glucose Leukocyte esterase Microscopic analysis (performed if blood, leukocytes, or protein are present)
Urine Drugs of Abuse b,c	Serology d	Other	
Barbiturates Cocaine Tetrahydrocannabinol Amphetamines Opiates Phencyclidine	HIV-1 HIV-2 HBsAg HCV antibody	Prothrombin Pregnancy test Follicle-stimulating hormone e Alcohol screen c	

- a. Fasting required at screening only
- b. At a minimum, these tests must be included
- c. During the screening period, urine drugs of abuse and alcohol screens may not be repeated for eligibility
- d. Includes any confirmatory tests performed at the discretion of the Investigator
- e. As needed to confirm postmenopausal status

For any laboratory test value outside the reference range that the Investigator considers clinically significant during the on-study period (ie, following dose administration), the Investigator will:

- Repeat the test to verify the out-of-range value and clinical significance.
- Follow the out-of-range value until the value returns to normal or baseline, or until the value is deemed stable and not clinically significant by the Investigator.
- Record as an AE any laboratory test value that is confirmed by repeat and the Investigator considers clinically significant, requires a subject to be discontinued from the study, requires a subject to receive treatment, or requires a change or discontinuation of the study vaccine (if applicable).

#### 7.7.4 Vital Signs

Vital signs assessments will include systolic and diastolic blood pressure (mmHg), heart rate (bpm), respiratory rate (breaths per minute), and oral temperature (C°). In addition, oral temperature will be performed prior to each vaccination. Vital signs will be measured after the subject has been resting quietly in a seated position for at least 5 minutes. Any clinically significant abnormal vital sign assessment requires at least one repeat measurement.

A vital signs abnormality that is considered clinically significant initially and on confirmation, requires a subject to be discontinued from the study, requires a subject to receive treatment, or requires discontinuation from the study vaccine (if applicable) will be recorded as an AE.

#### **7.7.5                   Physical Examination**

Comprehensive physical examinations (excluding genital, rectal, and breast examinations [unless indicated]) will be performed, and abnormal findings will be documented in the subject's eCRF.

Targeted physical examinations will focus on any AEs ongoing at the time of the examination ([Table 1-1](#)).

An abnormal physical examination finding that is considered clinically significant and requires the subject to be discontinued from the study, requires the subject to receive treatment, or requires discontinuation of the study vaccine (if applicable) will be recorded as an AE.

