### **3.2.2 Secondary Endpoints**

Safety:

- Unsolicited AEs, MAAEs, and AESIs up to Day 43
- SAEs, MAAEs, NOCDs, and AESIs up to Day 365 (approximately 1 year after first vaccination)

Immunogenicity:

- Vaccine ELISA of both RBD IgG and IgM antibodies and neutralizing antibody titers for each treatment group:
  - GMT at baseline and Days 15, 22, 43, 90, 181, 273, and 365
  - GMT ratio ( $GMT_{placebo}/GMT_{TAP-COVID-19}$ ) at baseline and Days 22, 29, 43, 90, 181, 273, and 365
  - GMFR at Days 8, 22, 29, 43, 90, 181, 273, and 365 relative to baseline
  - Seroconversion rates on Days 8, 15, 22, 29, 43, 90, 181, 273, and 365. Seroconversion is defined as the proportion of subjects at the respective time point that have detectable antibodies (IgG and IgM) against SARS-CoV-2 Spike Protein RBD following challenge with vaccine (and potentially by natural asymptomatic or symptomatic infection by the virus in case of a placebo subject).
  - GMI on Days 8, 22, 29, 43, 90, 181, 273, and 365

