## 8 ADVERSE EVENTS

An AE is defined as any untoward medical occurrence in a subject administered a pharmaceutical product during the course of a clinical investigation. An AE can therefore be any unfavorable and unintended sign, symptom, or disease temporally associated with the use of a study vaccine, whether or not thought to be related to the study vaccine. A TEAE is any AE that occurs after the first dose of study drug, regardless of relationship to the study drug.

MAAEs are AEs for which the subject has received medical attention by medical personnel, or in an emergency room, or which led to hospitalization. For each reported AE, the Investigator will ask the subject if such medical attention has been received. In addition, the Investigator will assess each MAAE if it constitutes a NOCD, defined as a MAAE that was:

- absent at baseline,
- not resolved at EOS
- required continuous medical care or attention.

Subjects will be monitored throughout the study for AEs, from the first dose of study vaccine through Day 43 of the study and for SAEs, MAAEs, NOCDs, and AESIs from the first dose through the end of the study (Day  $365 \pm 14$  days). Adverse events that are identified at the last assessment visit (or the early termination visit) as specified in the protocol must be recorded on the AE eCRF with the status of the AE noted. All events that are ongoing at this time will be recorded as ongoing on the eCRF. All (both serious and nonserious) AEs must be followed until they are resolved or medically stable, or until reasonable attempts to determine resolution of the event are exhausted. The Investigator should use his/her discretion in ordering additional tests as necessary to monitor the resolution of such events.

The procedures specified in [Section 8.4](#) are to be followed for reporting SAEs.

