**Table 8-1       DAIDS Adverse Events Intensity Assessment**

Grade	Intensity	Definition
Grade 1	Mild	Symptoms causing no or minimal interference with usual social and functional activities with intervention not indicated.
Grade 2	Moderate	Symptoms causing greater than minimal interference with usual social and functional activities with intervention indicated.
Grade 3	Severe	Symptoms causing inability to perform usual social and functional activities with intervention or hospitalization indicated.
Grade 4	Potentially Life-Threatening	Symptoms causing inability to perform basic self-care functions with intervention indicated to prevent permanent impairment, persistent disability, or death.
Grade 5		Any AE where the outcome is death

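### Section 7.7.5 makes a clinically significant examination finding an AE when it also requires treatment or discontinuation, which is narrower than the Section 8 definition and out of line with 7.7.3 and 7.7.4

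*Combined protocol and SAP*

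**What the plan says.** Section 7.7.5 tells sites to record as an AE an examination "finding that is considered clinically significant and requires the subject to be discontinued from the study, requires the subject to receive treatment", with stopping the study vaccine as the third listed action. Clinical significance is tied to the list of actions by *and*.

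The neighbouring sections are built differently. Section 7.7.3, in the text under Table 7-1, reads "Record as an AE any laboratory test value that is confirmed by repeat and the Investigator considers clinically significant" and continues with similar actions as further items in one series. Section 7.7.4 opens its rule with "A vital signs abnormality that is considered clinically significant initially and on confirmation" and gives the actions as alternatives. It also states: "Any clinically significant abnormal vital sign assessment requires at least one repeat measurement".

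Section 8 attaches none of these conditions: "An AE can therefore be any unfavorable and unintended sign, symptom, or disease temporally associated with the use of a study vaccine", related or not. Table 8-1 describes Grade 1 as "Symptoms causing no or minimal interference with usual social and functional activities with intervention not indicated", so the protocol expects some AEs that need no intervention.

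The endpoint concerned is in Section 3.2.2: "Unsolicited AEs, MAAEs, and AESIs up to Day 43". Section 3.1.2 compares the frequency of unsolicited AEs for each dose against placebo and for high dose against low dose. Section 7.7.1 refers AE monitoring to Section 8, but no text says which wording prevails where 7.7.3 to 7.7.5 depart from it.

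**The concern.** Section 8 gives the general definition and Section 7.7 gives the working instruction for each type of assessment. Where the instruction is narrower, staff completing the AE page may follow either one. A site that follows 7.7.5 leaves a significant but untreated examination finding off the page. A site that follows Section 8 enters it. Findings of equal clinical weight are also handled differently according to whether they come from an examination, a vital sign or a blood test.

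What is at stake is the consistency of the unsolicited-AE count. Section 9.8 plans no statistical tests, so the tabulated counts are themselves the result for this endpoint.

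**Working it through.** The documents state no event rate or other figure for this point, so there is nothing to reproduce. The check is a comparison of texts.

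**Step 1. The rules side by side.**

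| Situation | 7.7.5 examination | 7.7.4 vital signs | 7.7.3 laboratory | Section 8 |
|---|---|---|---|---|
| Clinically significant, no action | rule not met | AE if significant again on repeat | AE if confirmed by repeat (usual reading of the series) | no condition on action |
| Clinically significant, not confirmed, no action | rule not met (no repeat is mentioned) | rule not met | rule not met | no condition on repeat |
| Clinically significant and leads to treatment or discontinuation | AE | AE, repeat not needed for this limb | AE if confirmed by repeat | AE |

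The first row holds the conflict. A significant finding without action meets the rule in 7.7.4 and 7.7.3 once confirmed, but never meets it in 7.7.5.

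**Step 2. A test case.** At the Day 15 targeted examination the examiner finds a new sign that the subject has not noticed. The investigator judges it clinically significant and decides only to observe it. Section 8 makes it an AE; the 7.7.5 rule is not met. A vital-sign abnormality judged significant at first and again on repeat, and likewise only observed, is an AE under 7.7.4.

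**Step 3. How much falls into the gap.**

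- The complete examination is scheduled at screening only (Table 1-1), so it contributes no post-dose findings.
- Post-dose examinations are targeted. The Table 1-1 footnote says they include systems indicated by an AE complaint, and 7.7.5 says they focus on ongoing AEs. Most therefore follow an event already raised.
- Pain, erythema, induration and swelling are solicited on the Diary Card (Section 7.7.2 and Appendix A) and belong to the primary endpoint.
- Other symptoms come in through Diary Card Section 2, graded from Grade 1, and through nondirective questioning (Table 1-1 footnotes).

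These routes do not close the gap. The diary windows are Days 1 to 8 and 22 to 29, or 8 + 8 = 16 of the 43 days, leaving 43 − 16 = 27 days outside them. Targeted examinations on Days 15 and 43 fall in that remainder. Questioning and Diary Section 2 collect what subjects notice, not signs they are unaware of. The sentence in 7.7.5 that sends abnormal findings to the eCRF is attached to comprehensive examinations. Even if targeted findings are entered there too, a finding that is not on the AE page is not in the AE count.

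What is left is a post-dose sign that is examiner-detected, unreported, unsolicited and not acted on.

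**Step 4. Scale.** With 30 subjects planned per treatment group in each part (Section 9.1), one such subject changes the proportion with that event by 1/30 = 3.3 percentage points, or by 1/60 = 1.7 points if the parts are pooled. This is the weight of one subject, not an estimate of how many are affected.

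**The case against.** The best defence is that 7.7.5 lists findings that will be recorded and does not say *only*. Section 7.7.1 sends AE monitoring to Section 8, and Section 8.1 sends AEs to the AE page, so a careful site could record the untreated finding anyway. This stands as far as the wording goes: exclusion is the natural reading of 7.7.5, not its literal text. But the pointer in 7.7.1 does not say which rule prevails, and the contrast with 7.7.3 and 7.7.4 remains.

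The second defence is that other routes capture nearly everything. It is largely right, and it limits the point to the set reached in Step 3. A reader might infer that mild or transient vaccine effects in general are lost. The documents do not support that, because common local signs are solicited and reported symptoms enter by other routes.

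Third, the confirmatory repeat in 7.7.3 and 7.7.4 might be read as a further loss of real events. Section 7.7.3 gives its purpose as verifying the value and its significance, and in 7.7.4 it conditions only the clinical-significance limb. Counting a result that is normal on repeat as an AE is a debatable preference, not a correction this point needs.

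Fourth, Table 8-1 is a fallback for AEs that the main toxicity scale does not cover (Section 8.2.3). It illustrates that untreated AEs are expected, and should not carry more weight than that.

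**Conclusion.** The inconsistency is real and small. As written, 7.7.5 is narrower than Section 8 and differs from 7.7.3 and 7.7.4, so the unsolicited-AE count to Day 43 can depend on which section a site applies. This rests on the natural reading of *and* in 7.7.5 and on the absence of a precedence statement.

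Two stronger inferences should be resisted. One is that the vaccine-placebo difference is pulled towards zero. That would need a rate for such signs in each arm and the share left unrecorded. The documents give none of these, so neither size nor direction can be derived. The other is that halting rule 7 is weakened. That rule (Section 5.7.2) needs related events of Grade 3 or higher, for which Table 8-1 has intervention or hospitalization indicated. Such findings would generally meet 7.7.5 anyway, so the rule is essentially unaffected.

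Section 9 defers the analysis details to a separate SAP. Its AE derivation rules are not in the text available for this review and could not be checked.

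**What to change.** In 7.7.5 replace *and requires* with *or requires*, so that a new or worsened clinically significant examination finding is an AE whether or not it is acted on. Add one sentence stating that the Section 8 definition governs AE recording where 7.7.3 to 7.7.5 differ from it. Keep the repeat in 7.7.3 and 7.7.4, described as a check for measurement error.

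The cost is a wording change, a note to sites and a few more low-grade AE entries. No new procedure is needed. The summary of changes for version 9.0 says enrollment has stopped. For any subject already past Day 43, the clarification can act only through a check of documented examination findings against the AE page.

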#### **7.7.6                   Appropriateness of Safety Assessments**

Safety evaluations selected for this study are typical of those for this subject population and utilize widely accepted measures.

## 8 ADVERSE EVENTS

An AE is defined as any untoward medical occurrence in a subject administered a pharmaceutical product during the course of a clinical investigation. An AE can therefore be any unfavorable and unintended sign, symptom, or disease temporally associated with the use of a study vaccine, whether or not thought to be related to the study vaccine. A TEAE is any AE that occurs after the first dose of study drug, regardless of relationship to the study drug.

MAAEs are AEs for which the subject has received medical attention by medical personnel, or in an emergency room, or which led to hospitalization. For each reported AE, the Investigator will ask the subject if such medical attention has been received. In addition, the Investigator will assess each MAAE if it constitutes a NOCD, defined as a MAAE that was:

- absent at baseline,
- not resolved at EOS
- required continuous medical care or attention.

Subjects will be monitored throughout the study for AEs, from the first dose of study vaccine through Day 43 of the study and for SAEs, MAAEs, NOCDs, and AESIs from the first dose through the end of the study (Day  $365 \pm 14$  days). Adverse events that are identified at the last assessment visit (or the early termination visit) as specified in the protocol must be recorded on the AE eCRF with the status of the AE noted. All events that are ongoing at this time will be recorded as ongoing on the eCRF. All (both serious and nonserious) AEs must be followed until they are resolved or medically stable, or until reasonable attempts to determine resolution of the event are exhausted. The Investigator should use his/her discretion in ordering additional tests as necessary to monitor the resolution of such events.

The procedures specified in [Section 8.4](#) are to be followed for reporting SAEs.

### 8.1 Recording Adverse Events

Adverse events are to be recorded on the AE page of the eCRF. The following information will be recorded:

- Assessment of whether or not the AE is an SAE, MAAE, NOCD, or AESI ([Section 8.2.1](#))
- Assessment of AE intensity ([Section 8.2.2](#))
- Assessment of AE relationship to study vaccine ([Section 8.2.4](#))
- Action taken - dose not changed, vaccine dose 2 not given, not applicable, or unknown, as applicable
- Outcome - recorded as fatal, not recovered/not resolved, recovered/resolved, recovered/resolved with sequelae, recovering/resolving, or unknown, as applicable

## **8.2 Assessment of Adverse Events**

The Investigator will assess each AE for seriousness, intensity, and relationship to study vaccine.

### **8.2.1 Serious Adverse Events, Medically Attended Adverse Events, New Onset Chronic Medical Conditions, Adverse Events of Special Interest, and Potential Immune-mediated Conditions**

The Investigator is responsible for determining whether an AE meets the definition of an SAE, MAAE, NOCDs, or AESIs including potential immune-mediated medical condition from the first dose of the study vaccine through the end of the study (Day  $365 \pm 14$  days).

An SAE is any AE that results in any of the following outcomes:

- Death
- A life-threatening adverse drug experience
- Inpatient hospitalization or prolongation of existing hospitalization
- A persistent or significant disability/incapacity
- A congenital anomaly/birth defect

Important medical events that may not result in death, be life threatening, or require hospitalization may be considered an SAE when, based upon appropriate medical judgment, they may jeopardize the subject and may require medical or surgical intervention to prevent any of the outcomes listed in this definition. Examples of such medical events include allergic bronchospasm requiring intensive treatment in an emergency room or at home, blood dyscrasias or convulsions that do not result in inpatient hospitalization, or the development of drug dependency or drug abuse.

MAAEs are defined as hospitalization, an emergency room visit, or an otherwise unscheduled visit to or from medical personnel for any reason.

NOCDs are defined as any new ICD diagnosis (per current International Statistical Classification of Diseases and Related Health Problems) that is applied to the subject during the course of the study, after receipt of the study agent, that is expected to continue for at least 3 months and requires continued health care intervention.

AESIs are defined in Section 8.2.2 and a list of potential immune-mediated medical conditions is provided in [Appendix B](#).

Note: SAEs, MAAEs, NOCDs, and AESIs including potential immune-mediated medical conditions require immediate reporting to the medical monitor and/or Sponsor. Refer to [Section 8.4](#) for details.

### **8.2.2 Adverse Events of Special Interest**

An AESI is any AE that a regulatory authority has mandated be reported on an expedited basis (including to the iSRC), regardless of the seriousness, expectedness, or relatedness of the AE to

the administration of investigational product. To date, no AESIs have been identified specifically for the TAP-COVID-19 vaccine + CpG adjuvant. However, subjects who test positive for COVID-19, present with autoimmune disease, or are diagnosed with a potential immune-mediated medical condition ([Appendix B](#)) should be reported as AESI.

AESIs will be followed as per the procedures in the study protocol, SRM, and/or SAE SSP for SAEs and pregnancy reporting, regardless of the seriousness, expectedness, or relatedness of the AESI to the administration of study vaccine. AESIs will be reported by the site directly to the Sponsor, medical monitor, and SAE hotline at ICON (ICON Pharmacovigilance) ([Section 8.4](#)).

Subjects positive for SARS-CoV-2 will not be discontinued. Positive SARS-CoV-2 cases will be followed and include referral to a primary care physician, collection of all medical records, assessment of severity, and review by the site investigator and medical monitor. All positive SARS-CoV-2 cases will also be shared with the iSRC on an ongoing basis.

